## 1.9 Weight gain

There is emerging evidence from randomized trials that the use of integrase inhibitors could lead to significant increases in body weight. Two trials of raltegravir and three involving dolutegravir all observed greater weight gain increases in integrase containing regimens. These effects appear to vary by gender and race, with highest increases observed in women and those of black race. The mechanism for this needs to be fully elucidated. These data are from populations receiving treatment and more data is needed in healthy HIV uninfected populations using PrEP. HPTN 077 evaluated changes in weight and fasting metabolic parameters in 177 HIV-uninfected individuals randomized to cabotegravir or a placebo who had received at least one injection. No differences between study groups were found for change in weight or fasting metabolic parameters overall, or for subgroups. Among the 146 participants with paired weights, between W0 and W41 the median increase in weight for CAB treated participants was 1.1 (IQR -0.9, +3.0) kg compared to median 1.0 (IQR -1.2, +3.2) kg gained by PBO treated participants (=+0.1 kg, p=0.66). The distribution of weight changes across the 41 week treatment period did not

differ between CAB and PBO-treated participants, nor when divided into the oral phase ( $=+0.3$  kg,  $p=0.6$ ) and the injection phase ( $=+0.2$  kg,  $p=0.65$ ). A 5% or greater increase in weight from W0 to W41 was seen in 24 (22%) CAB participants and 7 (18%) of PBO participants ( $p=0.62$ ).

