### FOOTNOTES FOR APPENDIX I:

 Demographics may be collected and reported at either Screening or Enrollment.

 Staff are required to observe participants take one pill at Enrollment. If participants return with their pills at Weeks 2 & 4, staff will observe participant take one pill then as well, unless the participant has already taken oral study product that day. Participants must not be asked to take a second dose of oral study product for the sake of observation.

 Full physical exam is to be conducted during Enrollment. A targeted physical exam will be done at all other visits. Participant pulse, blood pressure and weight must be recorded at every visit. BMI must be calculated.

 The initial dose of the Hep B vaccination will ideally be given at Week 2, though there is flexibility around the timing of the vaccination. Subsequent doses may be given at different visits than indicated in this SOE, as long as sites follow manufacturer guideline timing.

 The HIV testing algorithm is provided in the SSP Manual. Testing for acute HIV must be negative and must be performed within the 14 days prior to enrollment of the participant. If HIV rapid testing is indicated, this testing may be performed in the clinic or the laboratory. At least one HIV assay result must be available and reviewed the same day as sample collection and before product is administered.

 Participants will be tested for Hepatitis B surface antibody (HBsAb), and Hepatitis B core antibody (HBcAb, total) at Screening or Enrollment. HbsAg and HCV Ab must be resulted and reviewed prior to enrollment.

 At Screening: Creatinine. At and after enrollment: BUN/urea, creatinine, CPK, calcium, phosphorous, glucose, amylase, and lipase.

 At Screening: ALT and TBili. At and after Enrollment: AST, ALT, total bilirubin, and alkaline phosphatase.

 Total cholesterol, HDL, triglycerides, and LDL (either calculated or measured). Participants must have fasted for at least 8 hours, preferably 12 hours, prior to sample collection. Do not collect or test if <8 hours fasting.

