## FOOTNOTES FOR APPENDIX II:

-  Medical history must include pulse, blood pressure, weight and Body Mass Index (BMI) calculated at each visit
-  The initial dose of the HBV vaccination is ideally given at Week 2, though there is flexibility around the timing of the vaccination. Subsequent doses may be given at different visits than indicated in this SOE, as long as sites follow manufacturer guideline timing.
-  The HIV testing algorithm is provided in the SSP Manual. If HIV rapid testing is indicated, this testing may be performed in the clinic or the laboratory. At least one HIV assay result must be available and reviewed the same day as sample collection and before product is administered.
-  BUN/urea, creatinine, CPK, calcium, phosphorous, glucose, amylase, and lipase.
-  AST, ALT, TBili, and alkaline phosphatase.
-  Total cholesterol, HDL, triglycerides, and LDL (either calculated or measured). Participants must have fasted for at least 8 hours, preferably 12 hours, prior to sample collection. Do not collect or test if <8 hours fasting. For participants who switch to Step 3 early (without having completed all 5 injections), the fasting lipid profile will be taken at the first visit after they transition off injections.
-  Stored plasma will be used for Quality Assurance testing and other assessments at the HPTN LC ([see Section 9](#)), including potential assay for plasma CAB concentrations.. Assessments will be performed retrospectively; results will not be returned to study sites or participants, except as noted in the SSP Manual. Samples cannot be used by site or other lab for local purposes without specific instructions from the LC w/ CMC consult.

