9.1 Adverse Events and Deaths

Adverse events of special interest (AESI) will be summarized in the Clinical Study Report. Planned AESI summaries for the CSR are described in Appendix A.

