13 CHANGE HISTORY

Version		Affected Section(s)	Activity Description
Number	Effective Date		
1.0	02/20/2021	All sections	First version of SAP was developed.
2.0	Date of last signature	2, 3, 6, 7-9, 11, 12, 13, 16, 17	Revisions based on new option to continue CAB injections during Step 3. Added study populations and definitions. Updated consort diagram, primary and secondary outcomes/analyses, including addition of secondary outcome 12.6. Updated acceptability endpoint definition, and reference to PK analysis plan. Additional details to account for changes to schedule of visits and data collection, due to new CAB option in Step 3. Added sections: 13 (ad hoc analysis), appendices A, B and C (AEs of special interest, variable definitions and imputation of missing data). Most revisions are designed to harmonize with HPTN 084-01 SAP 3.0.

14. APPENDIX A – Adverse Events of Special Interest

Adverse events of special interest (AESI) have been determined for CAB based on pre-clinical and clinical experience, along with information for the integrase inhibitor class of HIV medications safety profile. These are adverse events for which more detailed summaries of event characteristics are of interest.

The identification and classification of AESI will be based on MedDRA preferred terms as specified in the ADRG (Analysis Data Reviewers Guide). The current MedDRA version used for the preferred terms in the ADRG is v25.1. Preferred terms will be updated in the ADRG if a new version becomes available before the database lock.

Table 1 below shows the adverse events of special interest identified and reasons for including.

Table 1 Adverse Events of Special Interest (Clinical Study Report only)

AESI	Product Implicated	Reason for Including as AESI
Hepatic Safety Profile: Assessment of risk of hepatotoxicity	CAB	Clinical, Class, Regulatory Interest,
Hypersensitivity Reactions (HSR)	CAB	Class, Regulatory Interest,
Rash	CAB	Class, Regulatory Interest
Neuropsychiatric Events 
 • Suicidal Ideation/Behavior • Depression • Bipolar Disorder • Psychosis • Mood Disorders • Anxiety • Sleep Disorders 	CAB	Clinical, Class, Regulatory Interest,
Injection Site Reactions (ISR)	CAB	Clinical, Regulatory Interest
Seizures and Seizure-like events	CAB	Clinical, Regulatory Interest
Weight Gain	CAB	Clinical, Class, Regulatory Interest
Rhabdomyolysis	CAB	Clinical, Class, Regulatory Interest
Pancreatitis	CAB	Clinical, Therapeutic Area, Regulatory Interest

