Impact on Creatinine	CAB	Regulatory Interest, Therapeutic Area

Confidential

All proprietary rights reserved

Page 22 of 27

Hyperglycemia/new onset diabetes mellitus	CAB	Observation from 083, Class
---	-----	-----------------------------

Common ISR adverse events are defined by MedDRA preferred terms including injection site pain, injection site induration, injection site nodules and preferred terms of any other ISR exceeding the threshold as specified in the ADRG. ISRs will be explored regardless of IP relationship.

Each one of the AESIs described in Table 3 will be explored via the data listings in more detail. Listings will summarize Adverse events that occurred during Step 1 and/or Step 2 of the study and will contain information to assess the following.

Event Characteristics: The characteristics of all event occurrences during the post-baseline period will look at event characteristics (serious, drug-related, leading to withdrawal, or Grade 3/4, fatal), number of events per participant, outcome, maximum grade or intensity and action taken.

Time to First Event (TTFE) and Duration of Events: Time of onset and duration of event will be provided.

In addition, Pyrexia Plus includes PT: (Chills – 10008531, Feeling of Body Temperature Change - 10061458, Feeling Hot - 10016334, Body Temperature Increased - 10005911, Pyrexia - 10037660, Influenza Like Illness - 10022004, Fever – 10016558) events will be looked at in relation to timing of previous injection.

No formal summaries or statistical comparisons are planned for AESI.

15. APPENDIX B – Variable Definitions

1. CES-D-10 (score/categories)

Create a score based on 10 items below (in CASI questionnaire):

In the list below, please indicate how often you have felt this way during the past week by ticking the appropriate box for each question:

1. I was bothered by things that usually don't bother me.
2. I had trouble keeping my mind on what I was doing.
3. I felt depressed.
4. I felt that everything I did was an effort.
5. I felt hopeful about the future.
6. I felt fearful or afraid.
7. My sleep was restless.
8. I was happy.
9. I felt lonely.
10. I could not "get going", I did not feel motivated.

Scoring:

	Rarely or none of the time (less than 1 day)	Some or a little of the time (1-2 days)	Occasionally or a moderate amount of time (3-4 days)	All of the time (5-7 days)
--	--	---	--	----------------------------

Questions 5 & 8	3	2	1	0
All other questions	0	1	2	3

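### Weight Gain is an event of special interest found only through reported AE terms, while the weights recorded in Steps 1 to 3 have no planned summary after baseline

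*SAP*

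**What the plan says.** SAP Appendix A (section 14) lists Weight Gain among eleven adverse events of special interest (AESI), citing clinical, class and regulatory interest. On how they are found: "The identification and classification of AESI will be based on MedDRA preferred terms as specified in the ADRG". On how they are shown: each AESI "will be explored via the data listings in more detail", and "Listings will summarize Adverse events that occurred during Step 1 and/or Step 2 of the study". It closes with "No formal summaries or statistical comparisons are planned for AESI". SAP 9.1 reads more broadly, "Adverse events of special interest (AESI) will be summarized in the Clinical Study Report", but refers to Appendix A for the content.

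The protocol collects the measurement itself. For Step 1, Appendix I footnote 3 states "Participant pulse, blood pressure and weight must be recorded at every visit". For Step 2, Appendix II footnote 1 states "Medical history must include pulse, blood pressure, weight and Body Mass Index (BMI) calculated at each visit". Appendices III and IV attach the same footnote to the medical history row in Step 3.

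The SAP uses these data once. Section 7 summarises BMI, its age-standardised z-score and the resulting weight class at baseline, and leaves z-scores out of the clinical study report. Section 9.2 plans median and quartile change from baseline at follow-up for laboratory values. Section 9.3, Other Safety Measures, is a heading with no text.

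Protocol 1.9 explains the interest in weight: gain seen with other integrase inhibitors, and a need for more data in uninfected PrEP users. It gives measured results from HPTN 077, including "A 5% or greater increase in weight from W0 to W41 was seen in 24 (22%) CAB participants".

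**The concern.** An AE term enters the listing only if a site judges the change untoward and reports it. Neither document sets a measured threshold that would trigger a report. Participants are under 18 and still growing, so this filter can fail in two ways: a large gain may pass as expected growth, and ordinary growth may be reported as an event. The measured series would let a reader see which had happened, but it is not shown.

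The treatment of weight also differs from that of comparable AESI. Hepatotoxicity, rhabdomyolysis, pancreatitis, creatinine and hyperglycaemia each have a laboratory marker that SAP 9.2 summarises as change from baseline, so their listings are backed by measured data. Weight is also measured repeatedly and has no such summary.

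Finally, the study is meant to supply adolescent safety data alongside the adult trials. The HPTN 077 result in protocol 1.9 is measured change from W0 to W41, and a list of preferred terms has nothing to set against it.

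**Working it through.** **1. What is collected against what is analysed.** Visits are those where the medical history row is marked in protocol Appendices I to IV.

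| Phase | Scheduled weights | AESI listing | Summary of measured weight or BMI |
|---|---|---|---|
| Step 1 | Screening, Weeks 0, 2, 4 | covered | BMI at baseline only |
| Step 2 | Weeks 5, 6, 9, 10, 17, 18, 25, 26, 33, 34 | covered | none |
| Step 3, oral PrEP | +12, +24, +36, +48 | not covered | none |
| Step 3, CAB LA | +16, +24, +32, +40, +48 | not covered | none |

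The row is unmarked at +8 and at Early Discontinuation. A participant who completes the study has 2 + 10 + 4 = 16 or 2 + 10 + 5 = 17 weights after enrollment, none of which enters a planned summary.

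**2. The plan's own figures.** No precision is stated for weight. The only precision table is SAP Table 2, with half-width 1.96 × √(p(1−p)/50). It gives 0.083, 0.111, 0.127, 0.136 and 0.139 for p = 0.1 to 0.5, which match the printed values after rounding.

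Protocol 1.9 reports gains of 5% or more in 24 (22%) on CAB and 7 (18%) on placebo among 146 paired weights, p = 0.62. The split by arm is not given. Assuming 108 and 38: 24/108 = 22.2%, 7/38 = 18.4%, and an uncorrected chi-square gives p = 0.622. The cited figures are consistent with each other.

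**3. What a measured summary could show with nine enrolled (SAP 6.4).** Adult rates are used here as an assumption only; adolescents are growing and may differ.

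- Expected number gaining 5% or more: 0.18 × 9 = 1.6 at the placebo rate and 0.22 × 9 = 2.0 at the CAB rate. The difference is 0.04 × 9 = 0.36 of a participant.
- Chance that at least one of nine does so: 1 − 0.82⁹ = 0.83 and 1 − 0.78⁹ = 0.89. Even at adult rates some measured gain is likely, whether or not a site reports it.
- Exact (Clopper-Pearson) 95% intervals: 0/9 gives 0% to 33.6%; 2/9 gives 2.8% to 60.0%. At the planned size, 11/50 gives 11.5% to 36.0%.
- Mean change: the HPTN 077 CAB quartiles (−0.9, +3.0 kg) imply SD ≈ 3.9/1.349 = 2.89 kg if roughly normal. With t = 2.306 on 8 degrees of freedom, the 95% half-width is 2.306 × 2.89/√9 = 2.22 kg at n = 9, against 0.82 kg at n = 50. With an assumed SD of 5 kg for adolescents, these become 3.84 kg and 1.42 kg.

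**4. Alignment with HPTN 077.** Week 41 here is the +8 visit after the Week 33 injection (33 + 8), where no weight is scheduled. The nearest weights are at Week 34, then Week 45 (33 + 12) on oral PrEP or Week 49 (33 + 16) on CAB LA. A comparison with W0 to W41 is therefore approximate.

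**The case against.** The strongest reply is that weight appears in no objective or endpoint of either document. It is background in protocol 1.9 and one of eleven AESI, all handled alike, and a single arm of nine cannot separate a drug effect from growth. All of that is correct. It limits what the summary can claim, but it does not explain why a repeatedly measured safety variable is left out when laboratory values are not.

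Three stronger readings are tempting, and the documents support none of them.

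- A reader might infer that weight and BMI are never analysed. BMI is summarised at baseline; the gap is change over time.
- A reader might infer that the trial fails to answer a weight question of its own. It poses none as an objective, and attribution to CAB would stay out of reach after any fix.
- A reader might infer that HPTN 077 is the only adult evidence on weight. Protocol 1.9 also cites two raltegravir and three dolutegravir trials. Those are in treated populations, so HPTN 077 is still the PrEP result described there.

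Other coverage is possible. Protocol 6.1 requires AEs of Grade 1 and above to be recorded, so a site that sees gain as untoward would report it. SAP 2.2 allows exploratory work on laboratory and clinical data. The ADRG and the monitoring plan are separate documents and might specify a weight output. Neither the protocol nor the SAP names one; if it exists, the SAP should cite it.

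The case for z-scores is weaker than it looks. SAP Appendix B, item 4, directs the programmer to the girls' reference table, although all participants were assigned male at birth. The visit schedules require weight and BMI but do not name repeat height, so later BMI could rest on an outdated height. The SAP has also chosen to keep z-scores out of the clinical study report. These points stand and are reflected in the fix.

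**Conclusion.** The point holds as a gap in description. For Weight Gain, the SAP relies on reported AE terms in Step 1 and Step 2 listings and leaves 16 or 17 post-enrollment weights per completer without a summary. Gain that no site reports would be missed, and Step 3 is outside the listings altogether, although protocol 2.2 makes safety over the 48 weeks after the final injection a secondary objective and participants may continue CAB LA in that period.

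The effect on inference is small. With nine enrolled and no comparator, a count of 2/9 is compatible with anything from about 3% to 60%, and a mean change would be known only to within about 2.2 to 3.8 kg under the assumed SDs. The number injected is not stated and may be below nine. The benefit is a visible record of measured change that can be placed, loosely, beside the adult data.

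**What to change.** Add text under SAP 9.3:

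- Change from enrollment in weight, in kg and percent, at each scheduled visit through Week 34 and at the Step 3 visits where weight is recorded (such as +24 and +48): number, median, quartiles and range.
- The number with a gain of 5% or more, so that the HPTN 077 figure has a counterpart.
- Individual weight trajectories labelled by Step 3 product. With nine participants the plot will be more informative than quartiles within product groups.
- A statement that the output is descriptive and does not attribute gain to CAB. Keep the AESI listing as a supplement.

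Add change in BMI-for-age z-score, outside the clinical study report, only if the sponsor confirms that height is re-measured, and after Appendix B is changed from the girls' to the boys' table.

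The cost is one table and one plot from data the protocol already requires. The z-score part also needs the height check and the corrected reference.

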#### **5.7 Step 3, Follow-up Phase**

##### **Follow-up Phase**

All participants will be followed for 48 weeks following their last injection in Step 2 (per [Appendix III and IV](#)) and will have the choice of continuing on CAB LA or being provided with Tenofovir/Emtricitabine (Trade Name: TDF/FTC, Truvada®). If participants would like to switch from TDF/FTC to CAB LA in Step 3, that is allowable, but it will not lengthen Step 3.

Step 3 will begin with the +8 Week Visit, in which participants who received the Week 33 injection will return for a blood draw eight weeks afterwards, in order to complete PK monitoring of drug levels of CAB. Participants who do not receive the week 33 injection will have a +8 Week Visit after their last injection visit and continue to be followed per the Step 3 Follow-up Phase.

Both clinical and laboratory evaluations will occur during follow-up phase visits as well as CASI administration for either behavioral or acceptability assessments (see [Appendices III. and IV.: Schedule of Evaluations for Follow-up Phase – Step 3-Oral PrEP and Step 3-Injection](#)).

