# **6.0 SAFETY MONITORING AND AE REPORTING**

## **6.1 AE Definition and Reporting**

An AE is defined as any untoward medical occurrence in a clinical research participant administered an investigational product and which does not necessarily have a causal relationship with the investigational product. As such, an AE can be an unfavorable or unintended sign (including an

abnormal laboratory finding, for example), symptom or disease temporally associated with the use of an investigational product, whether or not considered related to the product.

Study participants will be provided a 24-hour telephone number and contact information and instructed to contact the study clinician to report any AEs they may experience. For life-threatening events, they will also be instructed to seek immediate emergency care. Where feasible and medically appropriate, participants will be encouraged to seek evaluation where the study clinician is based, and to request that the clinician be contacted upon their arrival. With appropriate permission of the participant, whenever possible, records from all non-study medical providers related to AEs will be obtained and required data elements will be recorded on study CRFs. All participants reporting an AE will be followed clinically, until the AE resolves (returns to baseline) or stabilizes.

Study site staff will document in source documents and the appropriate CRF all AEs [Grade 1 and higher, and any AE that leads to a study product hold (temporary or permanent) will be captured on CRFs] reported by or observed in enrolled study participants, regardless of severity and presumed relationship to study product. AE severity will be graded per the DAIDS Table for Grading Adult and Pediatric Adverse Events, Corrected Version 2.1, July 2017. This version will be used for the entire duration of the study.

The AE reporting period for this study is from Enrollment (Week 0) until follow-up in the study ends.

Relatedness is an assessment made by a study clinician of whether or not the event is related to the study agent. The relationship of all AEs to study product will be assessed as specified in Version 2.0, January 2010 of the DAIDS EAE Reporting Manual.

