**12.4 APPENDIX IV. SCHEDULE OF EVALUATIONS – FOLLOW-UP PHASE (STEP 3-INJECTION)**

WEEKS SINCE LAST INJECTION	Wk +8	Wk +16	Wk +24	Wk +32	Wk +40	Wk +48	Early Discontinuation
ADMINISTRATIVE, BEHAVIORAL, REGULATORY							
Locator information	X	X	X	X	X	X	X
HIV prevention & risk reduction counseling	X	X	X	X	X	X	X
Condoms per local SOC	X	X	X	X	X	X	X
Behavioral/Acceptability assessment (CASI)		X	X	X	X	X	X
CLINICAL EVALUATIONS & PROCEDURES							
Qualitative interviews continue (approximately)		X	X				
Medical history  , concomitant medications, targeted physical exam		X	X	X	X	X	
Hep B vaccination (if needed) 							X
Blood collection	X	X	X	X	X	X	
Urine collection			X			X	X
Rectal swab collection			X			X	
Injections (CAB LA)	X	X	X	X	X	X	X
ISR evaluation	X	X	X	X	X	X	X
Adherence counselling	X	X	X	X	X	X	X
LOCAL LABORATORY EVALUATIONS & PROCEDURES							
HIV testing 	X	X	X	X	X	X	X
CBC with differential			X			X	
Chemistry testing 	X		X			X	X
Liver function testing 	X		X			X	X
Syphilis testing			X				X
GC/CT testing (urine, rectal, and oral pharyngeal swabs)			X			X	X
Plasma storage 	X	X	X	X	X	X	
DBS storage		X	X		X	X	
HBsAb and HBcAb 						X	X
HCVAb						X	X

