2.1 General Design Considerations

HPTN083-01 is a phase IIB single arm trial designed to establish the minimum safety, tolerability and acceptability data needed to support the use of cabotegravir long-acting injection (CAB LA) in an adolescent population, potentially transforming the field of HIV prevention for young people. The study target population is sexually active, healthy male adolescents aged below 18 years. The study target is to enroll more than 50 participants with at least 50 participants receiving at least one injection. Participant recruitment will take approximately 12 months.

Study participation includes Step 1: a 5-week oral CAB 30mg QD safety lead-in followed by Step 2: a series of 5 intramuscular (IM) injections of 3 mL (600 mg) cabotegravir administered at 8-week intervals after a 4-week loading dose (injections at weeks 5, 9, 17, 25 & 33). Adherence support strategies (e.g., counseling, reminders, pill cases) will be included to support pill-taking during the first five weeks and to support retention during the injectable phase. A safety visit will follow each injection to ascertain pharmacokinetic-peak safety data, including injection site reactions. Step 3: A blood draw visit, the +8 Week Visit, will follow the week 33 injection to monitor CAB drug levels. All participants who have received at least one injection will be followed for 48 weeks after their last injection. Waning levels of cabotegravir (the PK tail) will be covered with locally sourced oral TENOFOVIR/EMTRICITABINE (TRADE NAME: TDF/FTC, TRUVADA®) for daily use for 48 weeks. In Step 3 participants may also choose to continue with 8-week dosing of injectable of CAB-LA for 48 weeks (5 additional injections beyond the initial 5 injections, administered at weeks +8, +16, 24, +32, +40, and +48.) Behavioral and acceptability data will be collected via computer-assisted self-interview (CASI). Total participant commitment for the entire study is up to 87 weeks, or approximately 1.5 years. We anticipate recruitment for the study will take approximately 12 months.

Participants who discontinue study product during Step 2 for any reason other than HIV infection or AE occurrence will be transitioned to open label TDF-FTC for 48 weeks.

There are in total three study sites:

- Adolescent and Young Adult Research at the Core Center (AYAR at CORE), Chicago, IL;
- St. Jude Children's Research Hospital CRS, Memphis, TN;
- Fenway Health CRS, Boston, MA.

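### The AESI listings stop at Step 2, so event-level detail on special-interest events in Step 3, when CAB LA may continue, is left out of the only AESI output planned

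*SAP*

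**What the plan says.** SAP section 9.1 sends the reader to one place: "Planned AESI summaries for the CSR are described in Appendix A". Appendix A (SAP section 14) names the AESI, among them hepatic events, hypersensitivity, rash, neuropsychiatric events, ISRs, seizures and weight gain. It then sets the scope: "Listings will summarize Adverse events that occurred during Step 1 and/or Step 2 of the study". It closes with: "No formal summaries or statistical comparisons are planned for AESI". The listings are therefore the whole AESI plan.

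Step 3 is not free of drug. Protocol section 5.7 lets participants choose between TDF/FTC and continued CAB LA. In Protocol Appendix IV, the row that begins "Injections (CAB LA" is marked at every visit from +8 to +48, and so is the ISR evaluation row. Protocol section 6.1 says: "The AE reporting period for this study is from Enrollment (Week 0) until follow-up in the study ends". Protocol section 2.2 lists safety over the 48 weeks after the final injection as a secondary objective.

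**The concern.** Events in Step 3 will be collected, but the stated filter keeps them out of the output written to describe them. ISR is itself an AESI, so ISRs evaluated at up to six Step 3 injection visits would not appear in the AESI listings. Participants who choose TDF/FTC are still in the drug tail: Protocol section 1.5.2 reports a median of 42.7 weeks to undetectable CAB in men in HPTN 077.

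What is at stake is event-level detail: seriousness, relatedness, grade, outcome, action taken, onset and duration. Enrollment stopped at nine participants (SAP section 6.4). In a group that small, the individual event record carries most of the safety information, and one late event matters.

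The SAP gives no reason for the limit. Its change history says that version 2.0 was prompted by the new option to continue CAB LA in Step 3, and that Appendix A was added in that version.

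**Working it through.** **1. The number of Step 3 injections.** SAP section 2.1 describes them as "5 additional injections beyond the initial 5 injections, administered at weeks +8, +16, 24, +32, +40, and +48". The stated count is 5, but six time points are listed. Counting from the last Step 2 injection at Week 33:

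- 33 + 8 = 41
- 33 + 16 = 49
- 33 + 24 = 57
- 33 + 32 = 65
- 33 + 40 = 73
- 33 + 48 = 81

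That makes 6, which agrees with the visits marked in Protocol Appendix IV. The stated 5 is not reproduced by the SAP's own list, and the two must be reconciled. Both are carried below.

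**2. Share of injections outside the listings**, for a participant who completes the 5 Step 2 injections and continues CAB LA:

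- by the listed visits: 6 / (5 + 6) = 6/11 = 54.5%
- by the stated count: 5 / (5 + 5) = 5/10 = 50%

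**3. Share of follow-up outside the listings**, for a participant who completes Step 2. The end of follow-up is Week 33 + 48 = 81. The step boundary is not stated consistently. Protocol section 5.7 says "Step 3 will begin with the +8 Week Visit", which is Week 41. Protocol section 2.3 puts the end of Step 2 at Week 34. SAP section 12.5 counts the +8 visit among the Step 1 and Step 2 visits.

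- boundary at Week 41: (81 − 41)/81 = 40/81 = 49.4%
- boundary at Week 34: (81 − 34)/81 = 47/81 = 58.0%

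**4. Who these shares do not describe.** Participants who leave in Step 1 have no Step 3. Early discontinuers have a different timeline: after the Week 5 injection alone, +8 is Week 13 and +48 is Week 53, so 40 of 53 weeks fall outside.

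**5. Ceiling for the trial.** If all nine accrued participants completed Step 2 and continued, Step 3 would hold at most 9 × 6 = 54 injections (9 × 5 = 45 by the stated count). The documents do not say how many continued.

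**6. What other outputs cover.**

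| Output | Reaches Step 3? | Event-level? |
|---|---|---|
| AESI listings, SAP Appendix A | No | Yes |
| EAE listing, Protocol 7.7.3 | No step limit stated; expedited reporting runs to end of follow-up (6.2.2) | Yes, expedited events only |
| ISR tables, Protocol 7.7.2 | No step limit stated | No |
| AE and SAE tables, Protocol 7.8.3 | Yes, aggregate includes follow-up | No |
| AE tables, SAP 3.2 | No step limit stated | No |
| Laboratory summaries, SAP 9.2 | No step limit stated | No |

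Protocol section 6.2.2 makes SAEs, any seizure, and combined ALT (at least 3 × ULN) and total bilirubin (at least 2 × ULN) elevations expedited. Those events in Step 3 belong in the protocol's EAE listing. What no planned listing covers is the rest: most ISRs, lesser liver elevations, rash, weight gain and non-serious neuropsychiatric events.

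**The case against.** The strongest reply is that the limit looks deliberate and that little is lost. SAP version 2.0 closes the primary safety window by Week 41 (8.1), labels the aggregate secondary safety window as Steps 1 and 2 (12.2), and does not carry the protocol's 48-week follow-up safety objective into its own list (2.2). Where the SAP wants Step 3 it says so, as in section 12.6 on drug resistance. The protocol prescribes no AESI listing, so no protocol rule on AESI is breached. The outputs in the table above also reach Step 3 or carry no step limit.

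Much of this stands, and it rules out three stronger readings that a reader might infer:

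- **That Step 3 special-interest events will be absent from the study report.** The documents do not support this. Expedited events have a planned listing and the others can be counted in tables. The SAP does not repeat the EAE listing, so whether it reaches the report is unclear, but unclear is not absent.
- **That CAB LA would be made to look safer.** The AESI listings estimate no rate and make no comparison. Any effect on a reported proportion would come from the analysis windows in SAP 8.1 and 12.2, which are a separate matter.
- **That Appendix A contradicts itself** by going on to speak of "The characteristics of all event occurrences during the post-baseline period". That phrase heads an item under the listing sentence and can be read within its Step 1 and 2 scope. The wording is loose, but it is not a clear conflict.

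A further limit applies to the count. The injection at +48 falls on the last scheduled visit and AE reporting ends with follow-up, so little would be observed after it.

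The reply does not explain why an exposure period with scheduled ISR evaluations should be left out of listings that include ISRs, and tables do not replace onset, duration and action taken.

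**Conclusion.** The point holds for the AESI listings. As written, they omit Step 3, and the firm loss is event-level detail for non-expedited special-interest events. This sits badly with the protocol's objective on safety for 48 weeks after the final injection.

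For a participant who completes Step 2 and continues CAB LA, up to 6 of 11 injections (55%) fall outside, or 5 of 10 (50%) by the SAP's stated count. The follow-up outside is 40 of 81 weeks (49%) with Step 3 starting at Week 41, or 47 of 81 (58%) with Step 2 ending at Week 34. These are maxima for that participant and not figures for everyone enrolled. They assume that the Step 2 injections fall on schedule and that follow-up runs to +48. If the +8 visit counts as Step 2, as in SAP 12.5, the first eight weeks of the tail are already inside the listings.

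This should be corrected. It changes no primary estimate.

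**What to change.** In SAP Appendix A, replace the restriction to Steps 1 and 2 with a window from enrollment to the end of follow-up. Flag each listed event by step and by product in use at onset (oral CAB, CAB LA or TDF/FTC). Days since the last CAB LA injection would be a useful but optional column. If the exclusion of Step 3 is intended, the SAP should instead give the reason and say where Step 3 AESI will be reported.

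Reconcile the count of 5 with the six listed time points in SAP section 2.1, and state one boundary between Steps 2 and 3 so that the step flag can be programmed.

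The main change costs one sentence in Appendix A and a change of filter in the listing program. It needs no new data.
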